## **Randomization**

After provision of consent, randomization is performed by the operating surgeon during the operation, the moment where it is ensured that onlay planar mesh is not superior to mesh-suture e.g. more/larger fascia defects than anticipated are not found. Random sequence generator with random block size (of maximum 10) will be used to create randomized sequences in 1:1 ratio. In all participating centers, a case of

sequentially marked opaque envelopes will be made available. The envelopes contain patient study ID, information on the assigned intervention group and the registration schematics along with information on when to perform registrations.

## Blinding

Patients will be blinded until the end of follow-up, which is planned to be 5 years.

[figure not shown]
### Blinding of trial participants:

Blinding is maintained by ensuring that the operative report only states: “... a mesh is implanted according to the study protocol and randomisation number ...”. This prevents patients from being able to see which type of mesh was used.

### Blinding of the assessing physician:

The physician who performs the follow-up assessment for wound complications is never the operating surgeon. Furthermore, the local database is configured so that the assessing physician does not have access to the section where the operating surgeon records the specific type of implanted mesh.

Furthermore, all surgeons involved will receive detailed information about entering relevant basic data in a local database (redcap) and all performed operations are registered in the Danish National Herniadatabase as well. All patients will be contacted by a nurse/study group member who is unaware of randomization results and treatment given in order to collect PROM data.

Investigational device	V1	V2	V3	TC1	JC3	TC2	JC4	TC3	JC5	TC4	JC6
Implant Duramesh vs standard mesh	x										
Safety assessment			x	x	x						
Patient-reported outcome	V1	V2	V3	TC1	JC3	TC2	JC4	TC3	JC5	TC4	JC6
European hernia questionnaire		x	x	x		x		x		x	
Socio-economic questionnaire (analgesic use, GP visit, return to work)		x	x	x		x		x		x	
Study team reported outcome	V1	V2	V3	TC1	JC3	TC2	JC4	TC3	JC5	TC4	JC6
Operation time		x		x							
Readmission				x	x	x	x	x	x	x	x
Recurrence				x	x	x	x	x	x	x	x

## Outcomes

### Primary outcome

1. Surgical site occurrences (SSO) on postoperative day 7-13. Definition: We will apply the standardized CDC (Centers for Disease Control and Prevention) and VHWG (Ventral Hernia Working Group) definitions for SSO (appendix 1). Evaluation: Clinical examination. Additionally, an ultrasound examination will be performed.

### Secondary outcomes

2. QoL on postoperative day 7-13 and day 90. Definition and evaluation: The EHS (European Hernia Society) validated EuraHS-quality-of-life (QoL) score (attached).

3. Duration of surgery (min).

### Sub-study 1: Long-term recurrence

In this sub-study we will assess hernia recurrence events in both study subgroups after 1, 3 and 5 years.

### Sub-study 2: Long-term outcomes

In this sub-study we will assess QoL as defined above in both subgroups after 1 year.

### Sub-study 3: Socio-economic aspects

In this sub-study we will assess socio-economic parameters (specifically time to return to work, analgesic use and contact with the primary sector) in both groups on postoperative day 7-13, 90 and after 1, 3 and 5 years.

### Study duration

Patient inclusion: 2 years from September 2025 - September 2027, plus 5 years follow-up.

## **Safety assessment and study termination**

Conversion of intervention to standard treatment: If, after randomization, interventional treatment is impossible to apply, then standard treatment will be performed.

The study will be terminated if the complication rate for patients operated with mesh suture exceeds known complication rates for planar mesh. Adverse events will be assessed and registered 7-13 days after surgery by clinical examination and 90 days after surgery by phone as well as by going through patient medical records.

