# BACKGROUND

Surgery for small ventral hernias (< 2 cm) is one of the most frequently performed operations in Denmark, with 2469 procedures performed in 2023. Despite it being a relatively small operation, up to 7.1% of patients are readmitted to emergency departments <90 days after surgery, primarily due to wound problems, and up to 2.2% of patients are reoperated <30 days after surgery. Historically, the two most important outcome measures following small ventral hernia repair are postoperative wound events and long-term hernia recurrence. Current standard treatment of these hernias in Denmark is open surgery with onlay planar mesh placement. With onlay planar mesh, the hernia sack is dissected and reduced, the abdominal wall defect closed with a non-dissolvable suture, subcutaneous tissue dissected from the underlying fascia and non-resorbable mesh implanted on top of the fascia. This method is proven superior to closure of the hernia defect with only a suture in terms of recurrence rates. There is, however, a higher risk of seroma/hematoma formation and wound infection when planar mesh is used compared to suture closure. Rates of postoperative seroma formation are reported to be as high as 46% and in our clinical practice, readmission to hospital is predominantly caused by seroma formation related to the operative site.

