Reported rates of surgical site occurrences (SSO) after operations for small ventral hernias vary greatly in the literature, additionally there is a lack of standardized definitions and reporting. In settings comparable to ours, one study from Sweden showed complication rates of 23.7% after onlay planar mesh repairs. The higher rate of hernia recurrence with suture only repair is attributed to the suture cutting through tissue (“cheese wire cutter effect/ or suture pull-through effect”), which occur when the sharp leading edge of the suture applies focused pressure at the suture/tissue interface and the pressure causes either abrupt cutting of tissue or a more gradual process of tissue ischemia and scarring, remodeling over time. In experimental studies, low suture tension has been found to promote more favorable collagen composition of the incisional region. Planar mesh implantation redistributes tension forces over a large surface area so the edges of fascia have optimal conditions for healing, but at the cost of higher wound complications rates and longer operation time.

Several methods have been developed to reduce fascial tension during healing without extensive dissection of suprafascial or subfascial tissue. Among those are mesh sutured repairs where 2 cm wide mesh strips are used to close fascial defects just as with single tread interrupted suture. Mesh sutured repairs showed promising results even in contaminated fields and larger defects. Mesh sutured technique is however subject to many variables that may alter its efficacy, such as accurate strip cutting, strip passing technique and mesh availability at the hospital.

Recently, a mesh suture has been developed (our proposed study intervention), with an attached needle and a tubular design with pores in the wall, combining functions of both suture and mesh, allowing ingrowth of tissue without capsule formation, while having the tensile strength nearly identical to those of a 0-

polypropylene suture. Available data support the safety and efficacy of this mesh suture for abdominal wall closure.

[figure not shown]

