### Study population and sample size

In the literature, wound complication incidences vary greatly (from 0.7 to 63.3%), at least in part due to a lack of standardized definitions and reporting. We know that in our department the readmission rate after small ventral hernia repair is 7% (data from the National Hernia Database, 2023). The majority of these readmissions is due to wound complications. We estimate that least as many patients are treated for minor SSO in primary sector as in the hospitals (unpublished data), so the true incidence of wound complications is estimated around 14 percent for onlay mesh.

In the literature the reported *surgical site event* rate for umbilical hernias is 2.4%, with infection rates of 4.9%. For ventral hernias, surgical site events range from 1% to 8.2%, while infections range from 3.1% to 5.2%.

It is also important to note the *wound classification* in the referenced study:

- **Umbilical hernias:** 14.6% were classified as *clean-contaminated*
- **Ventral hernias:** 18.6% *clean-contaminated* and 12.4% *contaminated*

In our study, all procedures are performed in an **outpatient setting** and involve only **clean wounds**.

Additionally, **13% of patients** in the referenced cohort were **active smokers**, despite smoking being a well-established risk factor for postoperative wound complications. In our study, the rate of active smoking is **0%**, as all participants are required to be smoke-free for at least **six weeks preoperatively**, with random testing performed to verify compliance.

Based on these distinctions, our *realistic* expectation for wound complications is **1–3%**. However, to remain appropriately conservative, we have chosen to report an estimated complication rate of **4%**.

A reduction in wound complications from 14% to 4% is considered clinically significant.

A sample size of 254 participants was determined to have 80% power to detect a clinically significant between-group reduction in surgical site occurrences (seroma/hematoma formations and postoperative wound infections) from 14 to 4% and a type I error of 5%, without increase in recurrences. This number was increased to 280 participants to account for conversions and cases lost to follow-up.

No interim analyses are planned. The planned sample size is 280 patients with equal assignment to the two groups.

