## **Statistical methods**

A sample size of 254 participants was determined to have 80% power to detect a clinically significant between-group reduction in surgical site occurrences from 14 to 4% and a type I error of 5%. This number was increased to 280 participants to account for conversions and cases lost to follow-up. No interim analyses are planned.

Data will be analyzed by a blinded analyst on an intention-to-treat basis, according to the prespecified statistical plan. A two-sided P-value  $< 0.05$  is considered significant.

Analysis of the primary outcomes: Depending on the distribution of data, continuous variables will be described with mean (SD, standard deviation) or median [interquartile range (IQR)] and analyzed with students t-test or Mann-Whitney U test, respectively. Categorical variables will be described as frequencies (%) and analyzed using Fisher's exact test.

Analyses will be conducted using Stata software.

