# ETHICAL CONSIDERATIONS

Potential benefits, risks and side-effects by participation

Use of mesh suture is simple and resembles standard suture use, thus all surgeons who perform ventral hernia repair would easily be able to use the technique.

A potential concern is a potentially higher recurrence rate among patients operated with mesh suture. We will review all collected data after 3 months by a project member not otherwise involved in the project, and if early (<90 days) recurrence rates in mesh suture subgroup exceed national average reoperation rates (2%), the study will be terminated. If recurrence appears, patients will be offered standard treatment with planar mesh. It is important to mention that reoperation in case of recurrence would be easy to perform due to lack of prior extensive dissection of subcutaneous tissue and thus less fibrosis.

Patients will expectedly be subject to increased awareness regardless of whether they are randomized to the intervention group or standard treatment, as this is a known phenomenon of study participation. This may make treatment safer in both groups.

Study participants will not receive financial compensation or other benefits and will be treated according to the Helsinki declaration. Complications directly attributable to the treatment will be eligible for insurance claims from the Danish public patient insurance (“Patienterstatningen”).

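### Both mandatory study-termination rules are badly fixed: the recurrence rule sets unlike events side by side with no allowance for chance, and the complication rule names no reference value

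*Protocol*

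**What the plan says.** The protocol contains two rules that end the study.

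- **Complications** (Safety assessment and study termination): "The study will be terminated if the complication rate for patients operated with mesh suture exceeds known complication rates for planar mesh". No reference value, event definition, time window, look time, minimum number of patients or responsible person is attached to it.
- **Early recurrence** (Ethical considerations): "if early (<90 days) recurrence rates in mesh suture subgroup exceed national average reoperation rates (2%), the study will be terminated". The look is described as follows: "We will review all collected data after 3 months by a project member not otherwise involved in the project". It is not said whether the three months run from the start of the trial or from each patient's operation.

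The figures that might serve as references are scattered. For wound complications, the sample-size section gives a literature range of 0.7% to 63.3% and then states that "the true incidence of wound complications is estimated around 14 percent for onlay mesh". The Background reports that "one study from Sweden showed complication rates of 23.7% after onlay planar mesh repairs" and mentions seroma rates of up to 46%. For reoperation, the only figure besides the 2% is in the Background: "up to 2.2% of patients are reoperated <30 days after surgery".

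Statistical methods states: "No interim analyses are planned". The sample-size section and the protocol summary say the same.

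**The concern.** Both rules are worded as obligations, so their exact terms decide whether the trial survives. The recurrence rule compares a raw proportion with 2%, and at small or moderate numbers a raw proportion passes 2% easily by chance. The comparison is also between unlike things: a recurrence need not be reoperated, and the 2% carries no time window. The complication rule cannot be carried out without first choosing a number. If that choice is made once data are visible, it can stop a device that performs well or excuse one that does not.

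At stake are the trial's answer, if it stops by chance, and the protection of participants, if the reference is so high that the rule never acts. Complications by arm also overlap the primary outcome (surgical site occurrences), so who looks, and when, matters for the trial's integrity.

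**Working it through.** **The plan's own figures.** The protocol gives no false-stop or detection probability for either rule, so there is none to reproduce. Its sample size does reproduce: 14% against 4%, two-sided 5%, 80% power and no continuity correction give 128 per arm, 256 in total, against 254 stated. It is not at issue here.

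**Inputs.** 280 patients, 140 per arm (sample-size section). Recruitment over 24 months (Study duration). Recurrence benchmark 2% (Ethical considerations). Design rates 14% and 4% (Statistical methods). Assumptions: even accrual, and true recurrence rates of 1% and 2%, because the protocol states no expected recurrence rate.

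**Recurrence rule.** The trial stops when x/n > 0.02. For n ≤ 49 one event suffices (1/49 = 2.04%). At n = 50, 1/50 is exactly 2%, so two are needed. At n = 140, 0.02 × 140 = 2.8, so three are needed.

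*Calendar reading.* 280/24 × 3 = 35 patients, about 17 in the mesh-suture arm.

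- At month 3 itself, patients have on average half of their 90 days. With constant hazard this is about 17/2 = 8.5 full patient-periods: 1 − 0.99^8.5 = 8% and 1 − 0.98^8.5 = 16%.
- Once all 17 have completed 90 days: 1 − 0.99^17 = 16% and 1 − 0.98^17 = 29%.
- Project management allows recruitment in as little as 12 months. That gives 280/12 × 3/2 = 35 mesh-suture patients, and 30% and 51% once their follow-up is complete.

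*Per-patient reading, one look at all 140.* P(stop) = 1 − P(0) − P(1) − P(2).

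- True 1%: 1 − 0.245 − 0.346 − 0.243 = 17%.
- True 2%: 1 − 0.059 − 0.169 − 0.240 = 53%.

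**Complication rule.** P(stop) = P(X > b·n) for X ~ Binomial(n, p), at a single look. The true rates are 4% (hoped for), 14% (equal to the planar-mesh design rate) and, as an illustration only, 28% (twice that rate).

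| Reference b | n | Events to stop | True 4% | True 14% | True 28% |
|---|---|---|---|---|---|
| 0.7% | 17 | 1 | 50% | 92% | >99% |
| 14% | 17 | 3 | 2.9% | 43% | 89% |
| 14% | 35 | 5 | 1.2% | 55% | 98% |
| 23.7% | 17 | 5 | <0.1% | 7.8% | 54% |
| 23.7% | 35 | 9 | <0.1% | 4.8% | 68% |
| 46% | 17 | 8 | <0.1% | 0.1% | 7.4% |
| 46% | 35 | 17 | <0.1% | <0.1% | 0.8% |

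At n = 17, a true rate twice the design value stops the trial almost surely or in 7% of cases, depending only on which of the protocol's own figures is taken.

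*Upper bound from repeated looks.* The chance of ever crossing 14% at a true 4%, with a look after every patient up to 140 (exact recursion), is 28% from the first patient, 5.8% from the 20th and 1.5% from the 35th.

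**The case against.** **A flat contradiction of the no-interim statement.** A reader might infer one. The text does not support that. The protocol summary follows the statement with a full analysis at 280 patients, so it reads as no early efficacy analysis. A safety stop against an external rate is a different thing and spends no type I error. What stands is that the two are not reconciled, and that the complication rule has no named reviewer.

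**Tiny denominators.** These hold for the recurrence rule only if the three months are calendar time. The day-90 call and record check make a per-patient reading just as plausible. That reading removes the small denominator but not the fault, as the result at 140 shows.

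**Continuous watching.** No section describes a look after every patient. The weekly database monitoring under Study monitoring concerns reports of operations and completeness of data, not rates by arm. The 28% is therefore only an upper bound.

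**A device performing as hoped is likely to be stopped for complications.** This is not supported. Against 14%, a single look stops a 4% device in 2.9% of cases at 17 patients and 1.2% at 35.

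**The 30-day window.** The 2% national average and the figure of up to 2.2% within 30 days may be different statistics. It cannot be asserted that the benchmark is a 30-day rate, only that its window is not given.

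**An unseen analysis or monitoring plan.** It could set look times. But the protocol itself fixes two mandatory triggers, and a later document cannot apply them as worded without supplying the missing reference or changing the comparison.

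**Conclusion.** The point holds. The recurrence rule is faulty on either reading of its timing. It compares unlike events, states no window for the benchmark and ignores chance. A true rate of half the benchmark leads to termination with probability 8% to 17% under the calendar reading at 24-month accrual or a single look at 140, and a true rate equal to the benchmark with probability 16% to 53%. These figures rest on even accrual, constant hazard for the partial-follow-up values, and assumed true rates of 1% and 2%.

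The fault in the complication rule is mainly that its reference is undefined. Chance stopping at the hoped-for 4% is small against 14% at a single look, but the protocol's own candidate figures turn the same data into opposite decisions. The no-interim statement needs reconciling with both rules but is not strictly contradicted. Because both stops are mandatory and rewording is cheap, this should be corrected before any look is taken.

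**What to change.** Reconcile the protocol summary, Background, sample-size section, Safety assessment and study termination, Statistical methods and Ethical considerations, so that they state:

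1. No efficacy interim analysis is planned, but arm-level safety looks are made for both rules by the uninvolved reviewer already named in the ethics section.
2. There is a small, fixed number of looks, set by the count of mesh-suture patients with completed follow-up.
3. For each rule, the same event over the same window stands on both sides, with one named reference value. That value is for the sponsor's clinicians to choose.
4. The trigger allows for chance, with its false-stop and detection probabilities reported. One example is an exact lower confidence limit above the reference, with its level set for the number of looks.

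The level matters. An unadjusted one-sided 95% limit checked after every patient from the 17th would still stop falsely in 13% of trials at a true rate equal to a 2% reference, and in 17% at a true rate equal to a 14% reference.

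The cost is protocol wording and a one-page monitoring table. The price in sensitivity is real. At 17 patients against 2%, the one-sided 95% exact limit needs two events (lower limit for 2/17 is 2.13%). This cuts false stopping at a true 2% from 29% to 4.5%, but at a true 6% the trigger fires only 27% of the time: 1 − 0.94^17 − 17 × 0.06 × 0.94^16. Case-by-case review of individual serious events must therefore continue alongside it.

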## **Statistical methods**

A sample size of 254 participants was determined to have 80% power to detect a clinically significant between-group reduction in surgical site occurrences from 14 to 4% and a type I error of 5%. This number was increased to 280 participants to account for conversions and cases lost to follow-up. No interim analyses are planned.

Data will be analyzed by a blinded analyst on an intention-to-treat basis, according to the prespecified statistical plan. A two-sided P-value  $< 0.05$  is considered significant.

Analysis of the primary outcomes: Depending on the distribution of data, continuous variables will be described with mean (SD, standard deviation) or median [interquartile range (IQR)] and analyzed with students t-test or Mann-Whitney U test, respectively. Categorical variables will be described as frequencies (%) and analyzed using Fisher's exact test.

Analyses will be conducted using Stata software.

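### The 80% power quoted at 254 participants belongs to an uncorrected chi-square test; the Fisher's exact test that the protocol names has about 75% there and needs 278 evaluable

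*Protocol*

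**What the plan says.** The power statement appears twice in the protocol, under Study population and sample size and again under Statistical methods: "A sample size of 254 participants was determined to have 80% power to detect a clinically significant between-group reduction in surgical site occurrences", with the change given as "from 14 to 4% and a type I error of 5" percent. The margin is explained as follows: "This number was increased to 280 participants to account for conversions and cases lost to follow-up". Allocation is equal: "The planned sample size is 280 patients with equal assignment to the two groups".

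The primary outcome is "Surgical site occurrences (SSO) on postoperative day 7-13", which each patient either has or does not have. Under Statistical methods, in the paragraph on the primary outcomes, the only test given for this type of variable is: "Categorical variables will be described as frequencies (%) and analyzed using Fisher's exact test". Significance is judged by "A two-sided P-value" below 0.05. The protocol does not say which test or formula produced 254.

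**The concern.** A sample size carries its stated power only for the test it was calculated for. At event rates as low as 4% and 14%, Fisher's exact test is clearly conservative and needs more patients than the usual normal-approximation formula suggests. If 254 came from that formula, the 80% does not apply to the planned analysis. The 26 additional patients, meant for conversions and losses, would then be making up for the test. No interim analysis is planned, so nothing in the protocol would bring this to light before the final result. At stake is a higher chance of missing a true fall from 14% to 4%: up to about 25% instead of the stated 20%.

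**Working it through.** **Inputs, all from the protocol.** SSO rates 14% and 4%; two-sided alpha 0.05; power 80%; equal arms; 254 evaluable (127 per arm); 280 randomised (140 per arm); reserve 280 − 254 = 26.

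**Step 1: reproduce 254.** The pooled normal-approximation formula, without continuity correction, is

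n per arm = [z(0.975)·√(2·p̄·(1−p̄)) + z(0.80)·√(p1(1−p1) + p2(1−p2))]² / (p1 − p2)²,

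with p̄ = (0.14 + 0.04)/2 = 0.09.

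- First term: 1.960 × √(2 × 0.09 × 0.91) = 0.793.
- Second term: 0.842 × √(0.14 × 0.86 + 0.04 × 0.96) = 0.335.
- n = (0.793 + 0.335)² / 0.10² = 127.4 per arm.

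Rounded down per arm this is 254; rounded up it is 256. Power by the same formula at 127 per arm is 79.9%. The stated figure is therefore reproduced, apart from rounding, as an uncorrected chi-square size. The other common formulas fit less well: unpooled 125 per arm (250), arcsine 119 (238), continuity-corrected 147 (294).

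**Step 2: power of the test that is named.** For each pair of event counts (x1, x2), take the product of the two binomial probabilities under 14% and 4%. Sum these over all pairs for which the test gives p < 0.05. This is exact and uses no approximation or simulation. Fisher's two-sided p-value was computed both by probability ordering and by doubling the smaller tail; the power was the same.

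| Evaluable per arm (total) | Fisher's exact | Uncorrected Pearson chi-square |
|---|---|---|
| 127 (254) | 75.2% | 82.3% |
| 133 (266) | 77.7% | 84.2% |
| 136 (272) | 78.9% | 85.1% |
| 138 (276) | 79.6% | 85.6% |
| 139 (278) | 80.0% | 85.0% |
| 140 (280) | 80.4% | 85.3% |

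**Step 3: what this does to the reserve.** Fisher needs 278 evaluable for 80%. That is 278 − 254 = 24 more than stated, so 26 − 24 = 2 patients remain for losses. Keeping the protocol's own reserve proportion (26/280 = 9.3%) on top of 278 would need 278 / (254/280) ≈ 306.5, or 308 in equal arms.

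**Step 4: true type I error.** The same enumeration with both arms at a common rate between 4% and 14% gives about 2.0–3.3% for Fisher (127 and 140 per arm). For Pearson chi-square it gives about 4.5–5.1%, with the highest value, 5.13%, at 138 per arm near a common rate of 9%.

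**The case against.** Several points on the other side carry weight.

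- **254 is not a miscalculation.** A reader might infer an arithmetic slip. The protocol does not support that: 254 is right for an uncorrected chi-square test, and the text never says it was computed for Fisher. The fault is that the number and the test do not belong together. This stands.
- **75% is a floor.** A reader might also infer that the trial runs at 75% power, or that the entire reserve is gone. The first needs all 26 reserve patients to be unevaluable; the second overstates 24 of 26. Analysis is by intention to treat, so converted patients stay in the denominator (conversion may dilute the effect but does not reduce N). Randomisation takes place during surgery and the outcome is read on day 7–13, which leaves little time for loss. The protocol gives no loss rate. At an assumed 3% (136 per arm) Fisher has 78.9%, and at an assumed 5% (133 per arm) 77.7%. This stands, and the size is best given as a range.
- **The 4% is meant to be conservative.** The protocol calls 1–3% its realistic expectation. At 14% against 3%, Fisher has 86.5% at 127 per arm. This softens the consequence but does not make the stated figure right, because the claim is made for 4%.
- **Fisher's test is valid.** It keeps the type I error below 5%, so no bias or false-positive risk follows. This stands and limits the severity.
- **Centre.** Because in each centre "sequentially marked opaque envelopes will be made available", a reader might conclude that the primary test has to be stratified by centre. The Randomization section does not say whether there are separate lists or whether allocation is stratified, and adjustment of this kind is commonly left to the statistical plan. A plain chi-square test already restores the power. Stratification is optional and not part of this error.

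A separate statistical plan does not remove the point, since the protocol itself fixes both the test and the power.

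**Conclusion.** The point holds as a mismatch between the sample-size method and the named test. For 14% against 4% at two-sided 5%, the stated 80% at 254 is 75.2% under Fisher's exact test. Fisher reaches 80% only with 278 evaluable, so 24 of the 26 reserve patients go to the test and 2 are left for losses. Actual power is about 75–80%: 80.4% with no losses, 75.2% if the whole reserve is lost.

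This rests on equal arms, on SSO analysed as a yes/no outcome, and on Fisher being the primary test, as the Statistical methods section reads. The 3% and 5% loss rates are assumptions. The shortfall is at most about 5 percentage points and does not threaten validity, so this should be fixed but is not critical.

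**What to change.** **Preferred.** In Statistical methods, name the uncorrected Pearson chi-square test as the primary test for SSO, report the risk difference with its 95% CI, and keep Fisher's exact test as a sensitivity analysis. The test then matches the calculation behind 254, and the 26 patients are again a reserve for losses. State in both sample-size paragraphs that 254 was computed for this test.

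**Alternative.** Keep Fisher and restate the power in both places: about 75% at 254 evaluable, and 80% only if at least 278 of the 280 are analysed. Keeping Fisher, 80% power and the same reserve proportion would instead mean about 308 randomised.

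**Cost.** The first two routes are edits of a few sentences, need no extra patients, and are best made before any outcome data are seen. The small price of the chi-square test is its reliance on a large-sample approximation, whose true size can exceed 5% by about 0.1 percentage point at these rates.
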